## List of abbreviations

|                  |   |
|------------------|---|
| AE               | adverse event   |
| ALT              | alanine aminotransferase  |
| ANOVA            | analysis of variance  |
| AST              | aspartate aminotransferase  |
| AUC              | area under the curve  |
| BP               | blood pressure bpm
beats per minute  |
| BUN              | blood urea nitrogen   |
| C max | maximal plasma concentration  |
| CPK              | creatinine phosphokinase  |
| CNS              | central nervous system  |
| CRF              | case report form  |
| EPI              | Human Insulin(Adrenalin)  |
| EU               | European Union  |
| GCP              | Good Clinical Practice  |
| GP               | General Practitioner  |
| HIV              | human immunodeficiency virus  |
| HPS              | HypoSpray® proprietary transdermal delivery system (TDS)  |
| ICH              | International Conference on Harmonization of Technical Requirements for Registration of Pharmaceuticals for Human Use |
| IUCD             | Intrauterine Contraceptive Device   |
| LDH              | lactate dehydrogenase   |
| LFT              | Liver Function Test   |
| MHRA             | Medicines and Healthcare products Regulatory Agency   |
| mm Hg            | millimeters of mercury  |
| NCR              | no carbon required  |
| NRS              | numerical rating scale  |
| OECD             | Organisation for Economic Co-operation and Development  |
| PI               | Principal Investigator  |

|                  |   |
|------------------|---|
| PK               | Pharmacokinetics  |
| RBC              | red blood cells   |
| REC              | Research ethics committee   |
| SAP              | Statistical analysis plan   |
| SAE              | Serious adverse event   |
| SGOT             | serum glutamic oxaloacetic transaminase (same as AST)                             |
| SGPT             | serum glutamic pyruvic transaminase (same as ALT)                                 |
| SUSAR            | serious unexpected suspected adverse reaction                                     |
| $T_{1/2}$        | plasma concentration half life  |
| TDS ® | Proprietary transdermal drug delivery system                                      |
| $T_{max}$        | time passed since administration at which the maximum plasma concentration occurs |
| WBC              | white blood cells (leukocytes)  |
| WHO              | World Health Organization   |

## 1.0 Synopsis

|   |  |
|---|--|
| Name of medicinal product/active substance | Levellor™ HypoSpray Human Insulin 100 IU/mL  |
| Title of the Study                         | A Multi-Dose, Cross-over, Phase 0 Dose Ranging Study to Compare Levellar HypoSpray Human insulin in Healthy Volunteers.  |
| Protocol Number/Clinical Phase             | Protocol No.: LEV 001-D-020521
Phase 0-1  |
| Chief Investigator                         | [name], D.O., M.P.H.  |
| Study Site                                 | Clinical Studies Unit  |
| Rationale                                  | 
A new formulation of Human Insulin (Levellor™ HypoSpray) utilizes the HDS HypoSpray® drug delivery system (HypoSpray Pharma, Florida, USA) which is a novel, proprietary transdermal technology, developed for use in pharmaceutical, cosmetic and over-the-counter products.
 
Transdermal administration combines a rapid onset of action with a convenient and patient-friendly, and in this case needle-less method of administration, which, it is believed, will provide enhanced safety as a more rapid and long lasting physiological-response alternative to the traditional SC Injectable route for the administration of Insulin.
 
This study will assess the volunteer response to increasing doses of Human Insulin Levellar HypoSpray at various doses p.r.n. compared against SC injection at various sites of application and under varied conditions.
 |
| Objectives                                 | 
The primary objective is to determine the amount of lowering serum glucose and dose response to a topically applied formulation of Human Insulin (Levellor™ HypoSpray) administered by spraying onto adult Healthy Volunteer subjects as compared to no treatment. A 2-week period of daily blood sugar monitoring and insulin dosing for 3 days then monitoring for 3 days following will form the baseline data for each subject.
 
The secondary objective is to evaluate the tolerability and local and systemic effects of Levellar™ HypoSpray.
   |
| Design:                                    | This is a non-randomized, open label single period, phase 0I study.  |

|                                    |  |
|------------------------------------|--|
| Duration of treatment:      | The maximum study duration is 20 days.   |
| Study Population:           | Adult Male patient volunteers aged 20 to 60 years.   |
| Main Criteria for Inclusion | 
 
1. Healthy Adult Males
 
2. 20 and 60 years of age, inclusive.
 
3. The subject has a serum protein A1C of less than 6.
 
4. The subject is willing and able to read, understand the Subject Information Sheet and provide written informed consent.
 
5. The subject has a body mass index (BMI) within 18-50 kg/m^2.
 
6. The subject is in otherwise good health as determined by medical history and physical examination.
 
7. The subject is a non-smoker.
 
8. The subject must agree to continue with daily serum glucose testing by means of a wearable blood glucose for the pharmacokinetic assessments.
 
9. The subject is willing and able to comply with all testing and requirements defined in the protocol.
 
10. The subject is willing and able to return to the study site for all visits.
 
 |

|  |  |
|--|--|
| Main Criteria for Exclusion:        | 
 
1. The subject has any relevant deviations from normal other than blood glucose in physical examination, electrocardiogram (ECG), or clinical laboratory tests, as evaluated by the investigator.
 
2. The subject has had a clinically significant illness within 30 days preceding entry into this study.
 
3. The subject has a history of significant neurological, hepatic, renal, endocrine, cardiovascular, gastrointestinal, pulmonary, or metabolic disease.
 
4. The subject has a known allergy or history of hypersensitivity to Human Insulin or similar modified Insulin compounds.
 
5. The subject has used any prescription medication that may interfere with the evaluation of study medication.
 
6. The subject has donated or lost a significant volume of blood (>450 mL) within four (4) weeks of the study, and their Haemoglobin concentration and hematocrit have not returned to within 5% of normal.
 
7. The subject has a history of substance abuse or a current positive urine drug screen or urine alcohol test.
 
8. Alcohol consumption greater than community norms (i.e. more than 21 standard drinks per week for males).
 
9. Subjects who have received an investigational drug or have used an investigational device in the 30 days prior to study entry
 
 |
| Concomitant Medication Restrictions | The intake of any medications (OTC or prescription) will be vigorously discouraged except as required to maintain health.  |
| Total expected number of subjects   | Sufficient volunteers will be recruited so as to obtain 5 completed subjects. Up to two additional subjects may be added.  |

|                   |  |
|-------------------|--|
| Study Drug | The investigational medicinal product is Human Insulin (Leveller HypoSpray L). Three dose ranges will be assessed: administered via sprays from a syringe. Doses will be calculated from what the literature reports is the low end of Healthy Volunteer Insulin Sensitivity. The 3 doses will be 0.075 IU/KG body weight, 0.1 IU/KG Body weight and 0.15 IU/KG Body Weight. This will result in dose ranges of 5 to 20 IUs. |
|-------------------|--|

|                                 |  |
|---------------------------------|--|
| Randomization            | Subjects will not be randomized. Sites of application: applied topically to the neck/chest arm, thigh area or inner aspect of a forearm.   |
| Dosage                   | Patients will receive dosing from the investigator and document blood sugar with a wearable Continuous Glucose Monitor (Libre 2) and will be dosed for 3 days. The monitor will be worn for 24 hours before the first dose and longer if available up to 7 days before beginning the study routine and 3 days after and receive the study drug via topical application for three days.   |
| Criteria for evaluation: | 
Pharmacokinetics
 
Primary pharmacokinetic variables
 
The primary pharmacokinetic variables include: the reduction of serum glucose from baseline and at typical post prandial spikes and the amount of insulin necessary to accomplish this reduction. In addition to 90% confidence intervals, the data will be summarized by medians, and maximum and minimum values. The elimination half-life of Insulin will be compared using non-transformed data and parametric techniques. Averages for the serum glucose and Post prandial excursions will be compared against averages for experimental periods.
  |
| Safety and Tolerability  | 
Adverse Events will be recorded throughout the study, at all visits and during any telephone calls.
 
Details on medical history and concomitant illnesses will be recorded on the day of screening by conducting a medical interview of subject or subject relative(s) and/or review of the subject's medical records. Any changes observed or reported during the study will be recorded.
 
A brief physical examination will be performed at Screening and at the Final Visit.
 
Clinical laboratory tests will be performed at Screening, and on the days of Human Insulin administration, serum glucose levels will be monitored by means of a wearable Continuous Glucose Monitor.
 |

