LEV 101-D-022521

NCT04857320

A Physician-Initiated Multiple-Dose, Single Period, Phase 0-I Dose Ranging Study to Examine Leveller™ HypoSpray Human Insulin Adult Healthy Volunteer Patients

Protocol No.: LEV 101-D-022521
ClinicalTrials.gov Reference NCT04857320

Criteria for evaluation: Statistical Analysis Plan

[figure not shown]
21st APRIL, 2021

Version 1.3

SPONSOR: Langford Research Institute

Principal Investigator: [name], D.O., M.P.H.

Approved by Langford Research Institutional Review Board April 21st, 2021

AMENDMENTS:

1.	2.	3.	4.
----	----	----	----

The information in this document contains trade secrets and commercial information that are privileged or confidential and may not be disclosed unless such disclosure is required by applicable laws and regulations. In any event, persons to whom the information is disclosed must be informed that the information is privileged or confidential and may not be further disclosed by them. These restrictions on disclosure will apply equally to all future information supplied to you, which is indicated as privileged or confidential. Copyright 2020 Transdermal Delivery Solutions Corp dba HypoSpray Pharma.

Criteria for evaluation: Statistical Analysis Plan	
Pharmacokinetics
 
Primary pharmacokinetic variables
 
The primary pharmacokinetic variables include: the reduction of serum glucose from baseline and at typical post prandial spikes and the amount of insulin necessary to accomplish this reduction. In addition to 90% confidence intervals, the data will be summarized by medians, and maximum and minimum values. The elimination half-life of Insulin will be compared using non-transformed data and parametric techniques. Averages for the serum glucose and Post-prandial excursions will be compared against averages for experimental periods.

---	---

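### Baseline is undefined and, read literally, includes the dosing days; define it from pre-dose data, report the post-dose return, and use a drift-adjusted untreated reference as a sensitivity analysis

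*Protocol*

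**What the plan says.** The primary objective (Protocol 1.0 Synopsis, Objectives) is glucose lowering and dose response "as compared to no treatment". The design is non-randomized, open label and single period, with five completed subjects and no concurrent untreated group. The comparison is therefore within subject and over time.

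Three places bear on the reference:

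- **Objectives row.** It begins with "A 2-week period of daily blood sugar monitoring" and goes on to say that "insulin dosing for 3 days then monitoring for 3 days following will form the baseline data for each subject".
- **Dosage row.** "The monitor will be worn for 24 hours before the first dose and longer if available up to 7 days" before the study routine, "and 3 days after and receive the study drug via topical application for three days".
- **SAP, primary pharmacokinetic variables.** Reduction is measured from baseline, and "Averages for the serum glucose and Post-prandial excursions will be compared against averages for experimental periods". Neither baseline nor experimental period is tied to particular days. No model, drift adjustment or carry-over assumption is given.

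**The concern.** The reference is the whole comparison in this design, and three readings of it are open. They give different answers from the same data.

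If the Objectives sentence is followed as written, the dosing days help to form the value that they are compared with, and the effect is diluted. If baseline means pre-dose days only, any steady change over the wear period (for example sensor drift, habituation, or altered eating while enrolled) is counted as drug effect, and more so for later doses. If pre- and post-dose days are simply averaged, drift still remains, and its sign depends on the length of the run-in.

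Without randomization, blinding or a control group, a return of glucose toward the untreated level after Day 3 is the only check inside the study that a fall was not due to time. The schedule collects those days, but neither document says how they enter the comparison.

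**Working it through.** **The plan's own figure.** "The maximum study duration is 20 days". The Objectives row gives 14 + 3 + 3 = 20 days, which matches. The Dosage row gives 1 + 3 + 3 = 7 to 7 + 3 + 3 = 13 days. The two rows describe different run-ins, so results are shown for n = 1, 7 and 14 pre-dose days.

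**Assumptions, not in the documents.** One dose per day on Days 1-3; pre-dose days end at Day 0; post-dose days are Days 4-6; the summary is the daily mean glucose; days are independent with equal variance s². No SD is given, so results are multiples of s².

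**Step 1: dosing days inside baseline.** Let the untreated mean be m and the average fall on dosing days be d. The mean over all n + 6 days is m − 3d/(n + 6). The measured fall is then d × [1 − 3/(n + 6)], so the loss is 3/(n + 6):

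- n = 1: 3/7 = 43%
- n = 7: 3/13 = 23%
- n = 14: 3/20 = 15%

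**Step 2: drift of b per day.** The bias on dose day k is b × (k − mean day of the reference). Pre-dose days have mean day −(n − 1)/2, that is 0, −3 and −6.5. Pre- and post-dose days pooled have mean day 3.75 for n = 1 and −0.6 for n = 7.

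| Reference | Dose 1 | Dose 2 | Dose 3 |
|---|---|---|---|
| Pre-dose, n = 1 | b | 2b | 3b |
| Pre-dose, n = 7 | 4b | 5b | 6b |
| Pre-dose, n = 14 | 7.5b | 8.5b | 9.5b |
| Pooled, n = 1 | −2.75b | −1.75b | −0.75b |
| Pooled, n = 7 | 1.6b | 2.6b | 3.6b |

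A longer run-in does not cure the bias, and nor does pooling. A fitted linear day term removes linear drift exactly. With n = 1 that term cannot be estimated from untreated days without Days 4-6.

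**Step 3: precision.** Against the plain pre-dose mean, the variance of dose day minus reference is s²(1 + 1/n). With N untreated days (pre plus post) and a linear term it is s²[1 + 1/N + (k − D)²/S], where D is the mean day and S the sum of squares about it. For n = 1 the days are 0, 4, 5 and 6, so N = 4, D = 3.75 and S = 20.75:

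- k = 1: 1 + 0.25 + 7.5625/20.75 = 1.61
- k = 2: 1 + 0.25 + 3.0625/20.75 = 1.40
- k = 3: 1 + 0.25 + 0.5625/20.75 = 1.28

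| Pre-dose days | Pre-dose mean | Pre + post, linear term (Doses 1/2/3) | Dose 3 − Dose 1: without and with the term |
|---|---|---|---|
| 1 | 2.00 | 1.61 / 1.40 / 1.28 | 2.00 and 2.19 |
| 7 | 1.143 | 1.116 / 1.141 / 1.179 | 2.00 and 2.02 |
| 14 | 1.071 | 1.113 / 1.134 / 1.159 | 2.00 and 2.01 |

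With n = 5 and 4 degrees of freedom (t = 2.132), the 90% half-width is 2.132 × √(variance/5). It goes from 1.35s to 1.21s/1.13s/1.08s for one pre-dose day, and from 1.02s to 1.01s/1.02s/1.04s for seven.

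**Step 4: carry-over.** A residual effect r on all of Days 4-6 pulls the fitted line toward the treated level. The shift is r times the summed weights of those days: 0.25r/0.43r/0.61r for n = 1 and 0.46r/0.57r/0.67r for n = 7. If r is confined to Day 4, the shift is 0.22r to 0.24r (n = 1) or 0.15r to 0.20r (n = 7). Dropping Day 4 removes only that second case. It costs some precision: 1.68/1.47/1.36 s² for n = 1 and 1.143/1.180/1.231 s² for n = 7.

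**Sensitivity to independence.** With first-order autocorrelation of 0.3 and generalised least squares, the post-dose days lower every dose-versus-untreated variance for n = 1 and n = 7. For n = 14 they do not for Doses 1 and 2 (0.97 to 0.99 and 1.10 to 1.12). At 0.6 all fall. Dose-versus-dose variance also falls under these correlations (n = 7: 1.76 to 1.68 at 0.3).

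**The case against.** Two stronger readings are tempting. A reader might infer that the post-dose days have no role. The Objectives sentence says otherwise: it puts them in the baseline data, and no passage restricts baseline to pre-dose days. What is missing is a usable definition. A reader might also infer that adding these days sharpens every dose contrast at no cost. The precision table contradicts this. Against the plain pre-dose mean, Dose 3 is worse with seven pre-dose days and all three doses are worse with fourteen. Dose-versus-dose contrasts are not sharper when days are independent.

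The strongest remaining objection is to the trend model. Drift is assumed rather than shown, it must be linear, and with a 24-hour run-in each subject's line rests on four points. The Protocol rationale itself anticipates a long-lasting response, so Days 4-6 may not be fully untreated, and dropping the first 24 hours does not protect against a longer residual. For an exploratory study with five completers, descriptive before, during and after averages are a defensible primary summary. This objection stands, and it is why the trend fit belongs in a sensitivity analysis.

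It can also be said that no analyst would really put dosing days into baseline. That is likely, but the SAP has no text that prevents it.

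**Conclusion.** The point holds as a defect of definition. Followed literally, the Protocol's baseline dilutes the average effect by 15% to 43%, depending on the run-in; this rests on equal weighting of days, no drift and no carry-over. A pre-dose-only baseline removes the dilution but is exposed to drift that grows with dose day and could pass for a dose response if doses rise by day.

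The post-dose days are worth using in two ways: as the within-study check on time, and to make drift estimable with a one-day run-in, where the variance also falls by 19% to 36%. With seven or fourteen pre-dose days their value is removal of linear drift bias, with little or no gain in precision. The size of any drift or carry-over is unknown from the documents.

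**What to change.** 1. Reconcile the Objectives row, the Dosage row and the SAP, including two weeks against 24 hours to seven days. Define baseline as the pre-dose monitor data, excluding the dosing days, and state which days are the experimental periods.
2. Report pre-dose, each dosing day and post-dose Days 4-6 side by side for each subject, with the change from Day 3 to the post-dose days.
3. Add a prespecified sensitivity analysis: each dosing day's departure from a line fitted to that subject's pre- and post-dose days, with and without the first 24 hours after the last dose. State the assumptions of linear drift and no carry-over, and the 0.25r to 0.67r shift if carry-over persists over Days 4-6.
4. State that the monitor record is retrieved after Day 6, since the Protocol contents list labels the discharge visit only as Day 4 or later.

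The cost is a few sentences of SAP wording, a corrected Protocol sentence and a small extra analysis. No data beyond those already planned are needed.

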## 2.0 Flow Chart

| Study Day
Activity            | Visit 1
Screening | Visit 2
First Dose | Visit 3
Second
Dose | Visit 4
Last Dose | Visit 5
Discharge |
|---|----------------------|-----------------------|---------------------------|----------------------|----------------------|
| Informed consent                        | X                    |                       |                           |                      |                      |
| Inclusion/exclusion criteria            | X                    | X                     | X                         | X                    | X                    |
| Demography                              | X                    |                       |                           |                      |                      |
| Medical history                         | X                    |                       |                           |                      |                      |
| Brief physical examination              | X                    |                       |                           |                      |                      |
| Vital signs                             | X                    | X                     |                           | X                    | X                    |
| Concomitant medication                  | X                    | X                     |                           | X                    |                      |
| Local skin evaluation: clinical         | X                    | X                     |                           | X                    |                      |
| Hematology, biochemistry and urinalysis | X                    | X                     |                           | X                    |                      |
| Serum Glucose Profile Test*      | X                    | X                     | X                         | X                    | X                    |
| Urine Drug Screen                       | X                    |                       |                           |                      |                      |
| Randomization                           | X                    |                       |                           |                      |                      |
| Topical Dose                            |                      | X                     | X                         | X                    |                      |
| Patient Questionnaires                  |                      |                       |                           |                      | X                    |
| Adverse events                          |                      | X                     | X                         | X                    | X                    |

\* Normal pre and post meal and pre- and post bedtime Time Points as measured by the CGM

**A Physician-Initiated, Multiple-Dose, Single Period,  
Phase 0-I Dose Ranging Study to Examine  
Levvellor™ HypoSpray Human Insulin Adult  
Healthy Volunteer Patients  
VOLUNTEER DOCLOSURES**

Protocol No.: LEV 101-D-022521  
ClinicalTrials.gov Reference NCT04857320

[figure not shown]
21st APRIL, 2021

Version 1.3

SPONSOR: Langford Research Institute

Principal Investigator: [name], D.O., M.P.H.

Approved by Langford Research Institutional Review Board April 21st, 2021

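### As charted, Visit 3, one of the three dosing visits, has no skin evaluation and no vital signs, and no skin evaluation follows the last dosing day, although tolerability is the secondary objective

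*Protocol*

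**What the plan says.** The Synopsis (Protocol section 1.0, Objectives) states: "The secondary objective is to evaluate the tolerability and local and systemic effects of" the product. The Rationale adds that response will be assessed "at various sites of application and under varied conditions", and the Randomization entry says that the product is "applied topically to the neck/chest arm, thigh area or inner aspect of a forearm". Neither entry says which dose goes to which site.

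The Flow Chart (section 2.0) has five visits: screening, three dosing visits and discharge. The contents list gives Visit 3 as Day 2, Visit 4 as Day 3 and Visit 5 as Day 4 or later. The topical dose is marked at Visits 2, 3 and 4. The row "Local skin evaluation: clinical" is marked at Visits 1, 2 and 4. Vital signs are marked at Visits 1, 2, 4 and 5.

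Other safety capture is planned. The Synopsis says: "Adverse Events will be recorded throughout the study, at all visits and during any telephone calls". The chart marks adverse events at Visits 2 to 5 and questionnaires at Visit 5. The Synopsis also says: "A brief physical examination will be performed at Screening and at the Final Visit". The chart marks that examination at Visit 1 only.

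**The concern.** For a product sprayed on the skin, the skin evaluation is the chart's one row dedicated to local effects, and vital signs are a basic systemic measure. As charted, the second dosing visit contributes neither to the secondary objective. The skin row also ends on the last dosing day, so a reaction first visible at discharge has no charted evaluation.

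An adverse-event form does not replace a scheduled examination. When nothing is entered, the reader cannot tell whether the site was examined and clear or was not examined.

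A check at Visit 4 recovers the Visit 3 skin information only in part. If application sites differ between doses, location could separate a second-dose reaction from a third-dose one. If the same site is reused, it could not. The available text does not settle which applies. Nothing at Visit 4 recovers Visit 3 vital signs.

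**Working it through.** The plan states no figure to reproduce, so the check is a count of chart cells.

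**Inputs.** Chart marks are from Protocol section 2.0. Sample size is from the Synopsis: "Sufficient volunteers will be recruited so as to obtain 5 completed subjects. Up to two additional subjects may be added". That gives n = 5, or n = 7 with both additional subjects. The unit is the subject-visit, because the text does not fix the number of administrations per visit.

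| Row | V1 | V2 | V3 | V4 | V5 |
|---|---|---|---|---|---|
| Topical dose | | X | X | X | |
| Local skin evaluation | X | X | | X | |
| Vital signs | X | X | | X | X |
| Adverse events | | X | X | X | X |

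**Is the table intact?** Yes, as far as can be seen. Other rows carry marks at Visit 3 (eligibility, glucose profile, dose, adverse events) and at Visit 5 (vital signs, glucose profile, questionnaires, adverse events). The blanks are not a lost column.

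**Dosing visits with neither assessment.** Visit 3 is 1 of 3.
- n = 5: total 5 × 3 = 15; neither charted 5 × 1 = 5, so 5 of 15.
- n = 7: total 7 × 3 = 21; neither charted 7 × 1 = 7, so 7 of 21.

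The fraction is one third at any sample size.

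**Skin evaluations after the last dosing day.** Visit 5 is the only later visit and is unmarked: 0 of 5 subjects (0 of 7).

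**Coverage from first dose to discharge (Visits 2 to 5).** Subject-visits: 5 × 4 = 20, or 7 × 4 = 28.

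| Row | Visits marked | n = 5 | n = 7 |
|---|---|---|---|
| Local skin evaluation | 2 of 4 | 10 of 20 | 14 of 28 |
| Vital signs | 3 of 4 | 15 of 20 | 21 of 28 |
| Adverse events | 4 of 4 | 20 of 20 | 28 of 28 |

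**After the fix.** Skin evaluation and vital signs both reach 20 of 20 (28 of 28). The increase is 20 − 10 = 10 (28 − 14 = 14) skin evaluations and 20 − 15 = 5 (28 − 21 = 7) sets of vital signs.

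**The case against.** The strongest reply is that the governing text is not available. The contents list names sections on skin evaluation (9.1) and vital signs (9.2), a skin reaction scale (Appendix 4), and procedures for Visits 3 and 5 (5.1.3, 5.1.5, 5.4.3, 5.4.5). Timing would be expected there. The chart is also known to be unreliable: it omits the Final Visit examination and marks randomization in a trial that is not randomized. This limits the finding to the chart and Synopsis. It does not remove it: if those sections do schedule the assessments, the chart contradicts them and the same cells need correcting.

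A second reply is that a lighter middle visit may be intended, since concomitant medication and laboratory tests also skip Visit 3. That is possible, but the available text gives no such rationale, and it would not explain the missing skin evaluation at discharge.

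A third reply is that other capture is substantial. Adverse events are recorded throughout, "Patients will receive dosing from the investigator", a persisting second-dose reaction meets a skin check at Visit 4 a day later, and Visit 5 has vital signs, questionnaires and, per the Synopsis, an examination. This stands as a limit on the consequence. The main remaining gap is a transient skin or vital-sign change on Day 2, or a new skin reaction at discharge, that nobody records as an adverse event. None of these sources is said to include an examination of the application site.

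Finally, the counts restate one visit in three and two in four, and the SAP contains no tolerability analysis that they would alter. That is correct: they measure planned data collection and not bias.

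**Conclusion.** The concern holds. It should be corrected, but it does not touch the primary analysis. One of three dosing visits has neither assessment charted, and no subject has a charted skin evaluation after the last dosing day. No effect on any estimate is claimed.

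The conclusion rests on the chart being read as printed and on the Synopsis; confidence is medium because the detailed sections could not be checked. The documents do not assign dose levels to visits, so it cannot be said which dose level would lack the assessments. Nor does the chart say whether the Visit 4 skin evaluation comes before or after that day's dose.

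**What to change.** 1. In the Flow Chart, mark local skin evaluation at Visits 3 and 5 and vital signs at Visit 3.
2. Reconcile the chart with sections 5.1.3, 5.1.5, 5.4.3, 5.4.5, 9.1 and 9.2. Reconcile the physical-examination row with the Synopsis, which places that examination at Screening and the Final Visit.
3. List skin findings by dosing visit, dose given and application site, including discharge. With 5 to 7 subjects this is a descriptive listing, and the main point does not depend on it.
4. Leave adverse-event recording as it is.

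At one assessment per visit, the cost is 10 skin evaluations and 5 sets of vital signs for 5 subjects, or 14 and 7 for 7 subjects. All fall at scheduled visits and use procedures already in the chart, so no visit or procedure is added.
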